Date: April 1, 2021

Official title of the study: Pneumococcal nasopharyngeal and oropharyngeal carriage in adults older than 50 years of age in outpatient health care facility in Novi Sad

NCT04831788

Institution Name	University of Novi Sad, Medical Faculty	
Investigator Contact Information: - Full address - Phone No. - Fax No. - e-mail address	Name:	[name]
	Title:	Professor, MD, PhD
	Address 1	[name]
	Address 2	[name]
	City, ST, Zip	21101 Novi Sad, Serbia
	Phone/[contact]/ [name]
	E-mail:	[contact]

STUDY PROTOCOL

Objectives and hypothesis

Primary objective:

- To analyze overall serotype distribution of *Streptococcus pneumoniae* nasopharyngeal and oropharyngeal carriage among adults older than 50 years of age in the city of Novi Sad

Secondary objectives:

- To determine serotype on NP and OP carriage with pneumococcal serotypes among adults older than 50 years of age in the city of Novi Sad according to specific clinical indications set for the PPV or PCV

Clinical hypotheses.

- *Streptococcus pneumoniae nasopharyngeal and oropharyngeal carriage among adults older than 50 years of age in the city of Novi Sad is most probably present in less than 10% of the total population.*
- *Streptococcus pneumoniae serotypes covered by PPV or PCV are represented by more than 60% and 50% of the serotypes in overall distribution among tested subjects.*

Study design

Research center(s):

The research will be carried out by the:

1. Institute of Public Health of Vojvodina
 - Centre for Disease Control and Prevention and the Centre for Microbiology
2. Health Care Centre of Novi Sad
 - Department of General Medicine.

Patients

A prospective study will be conducted. We will sample the population based on voluntary participation. The target group of the research will be all adults who will visit their elected physicians in the Health Care Centre of Novi Sad (outpatient care facility). Only adults older than 50 years of age from Novi Sad with 341,624 (2011 Census) inhabitants will be recruited in this research.

All patients older than 50 years of age will be interviewed by physicians at the admission.

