To obtain DNA extracts for PCR reactions, an overnight growth of blood agar plate will be suspended in 300 µl of 0.85% NaCl, heated to 70 °C for 15 min, spun for 2 min and supernatant will be removed. Pellet will be suspended in 50 µl TE buffer with an addition of 10 µl mutanolysin and 8 µl of hyaluronidase, kept at 37°C for 30 min (to overnight), heated for 10 min at 100°C and spun for 4 min. No more than 2,5 µl of supernatant will be used as DNA template. Extracts will be stored at -20°C until PCR testing (9).

Identification of *S. pneumoniae*

Identification of *S. pneumoniae* will be achieved by amplifying the *lytA* gene using primers and probes recommended by CDC and Quanta Biosciences PerfeCTa1 qPCR ToughMix1, Low Rox™ (Quanta Biosciences, Beverly, USA) (10). LytA positive samples will be further analyzed for serotype identification.

Serotype identification

Conventional multiplex PCR assays will be performed as a series of multiplex reactions, using CDC recommended schemes and primers for pneumococcal serotype deduction and 2X PCR Buffer - QIAGEN Multiplex PCR Kit (Qiagen, Hilden, Germany). The PCR products will be analyzed on 2% NuSieve agarose gels (Cambrex Bio Science, Inc., Rockland, ME), stained with ethidium bromide. Gel images will be recorded BioDocAnalyze system (Analytik Jena, Jena, Germany).

Real Time PCR will be performed optionally in case of any difficulties with conventional PCR. It will be performed, as a series of 21 monoplex assays encompassing 21 serotypes using CDC recommended schemes based on geographic prevalence of serotypes. The assays are multiplexed in a sequential triplex format (three targets/serotypes in one reaction), each detecting targets on FAM, Rox (or Cy5) and Hex channels. Reactions will be performed on ABI 7500 Instruments (Thermo Fisher Scientific, Waltham, USA), using specific primers and probes and Invitrogen-Platinum Quantitive PCR SuperMix (Thermo Fisher Scientific, Waltham, USA).

Susceptibility testing

Susceptibility of Spn isolates to Optochin, Oxacilin, Norfloxacin, Erytromycin, Clindamycin, Tetracycline and Trimetroprim-sulfometoxazole will be determined by the Diffusion method according to the European Committee on Antimicrobial Susceptibility Testing (EUCAST, www.eucast.org).

This baseline assessment is taking into consideration to present descriptive only current results, but they are not separately taken into account for comparative analysis.

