The results of laboratory testing, conducted for each patient, will be forwarded to elected physicians who indicated sampling of patient material.

Study procedure

Adults will be recruited during their health examination at Health Care Centre of Novi Sad by their elected physician.

After providing a verbal and written explanation of the research aim (Appendix 1), informed consent (Appendix 2) will be obtained from subjects before enrolment. Personal and confidential information obtained from participants will be removed, except for demographic information, including date of sampling,

age, gender, data on previous upper respiratory tract infection, number of children (siblings) aged 0–10 years residing in the household of participants with pneumococcal and influenza immunization history (because influenza immunization may prevent pneumococcal superinfections), smoking habits of participants and their household members and the information about home residence (Survey Questionnaire- Appendix 3).

Samples will be provided as one NP swab per study subject. Every participant will be assigned only once. Confirmed case is every laboratory tested participant in which, after testing (PCR or ELISA), a positive result is obtained.

Statistical Analysis and Sample Size Justification

Collection of the data

Characteristics of all respondents acquired by questionnaire from Novi Sad, the test results of laboratory testing of samples of participants and the final characterization of *Spn* serotypes will be entered in specially designed database. Personal information of participants will be removed.

Investigator of the research along with statistician will analyze the collected data.

Sample size justification

In accordance with the sample size calculation for a study estimating a population prevalence (11), between 350 and 500 samples are planned to be collected. If more than 500 will be eligible they will all be included. We presume to detect pneumococci in up to 10% PCR-positive to *Spn*. Total number of adults older than 50 years of age is around 120,000, and therefore we expect to collect the sample up to 0.4% of the total targeted population.

Expected results

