After carefully implementation of the research, we expected that *Spn* carriage among adults older than 50 years of age will be present in less than 10% of the total population. In addition, we presume that *Spn* serotypes covered by PPV or PCV will represent more than 60% and 50% of the serotypes in overall distribution among tested subjects.

Statistical Methods

We will examine associations between risk factors and NP and OP carriage of pneumococci in participants aged older than 50 years. The following factors will be examined as possible risk factors in covered population: age, gender, data on previous upper respiratory tract infection, number of children (siblings) aged 0–10 years residing in the household of participants with pneumococcal and influenza immunization history, smoking habits of participants and their household members and the information about home residence. These factors will be analyzed by univariate and multivariate analyses (if appropriate). Also, the prevalence of NP and OP carriage as the proportion of participants whose nasopharyngeal cultures were positive for *Spn* and corresponding 95% confidence intervals will be estimated. All descriptive analyses will be performed using the SPSS Statistics software Version 21.0 (IBM Corp., Armonk, NY, USA).

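### Serotype distribution is the primary objective, but 95% confidence intervals are planned only for carriage prevalence; the PPV and PCV shares would be bare percentages of at most about 35–50 expected carriers

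*Combined protocol and SAP*

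**What the plan says.** - **Primary objective:** "To analyze overall serotype distribution of" pneumococcal NP and OP carriage in adults over 50.
- **Clinical hypotheses:** the first puts carriage below 10%. The second is that "serotypes covered by PPV or PCV are represented by more than 60% and 50% of the serotypes in overall distribution among tested subjects". Expected results repeats both. I read 60% as belonging to PPV and 50% to PCV, in the order listed.
- **Statistical Methods:** this section covers risk factors for carriage and "the prevalence of NP and OP carriage as the proportion of participants whose nasopharyngeal cultures were positive for" *S. pneumoniae*, for which "corresponding 95% confidence intervals will be estimated". It does not mention serotypes, a vaccine-type share, a denominator for that share or an interval for it.
- **Sample size justification:** "In accordance with the sample size calculation for a study estimating a population prevalence (11), between 350 and 500 samples" are planned. It adds "We presume to detect pneumococci in up to 10% PCR-positive to" *Spn* and "If more than 500 will be eligible they will all be included".
- **Identification of *S. pneumoniae*:** "LytA positive samples will be further analyzed for serotype identification". Serotype information therefore comes from carriers only.

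**The concern.** The quantity named as primary has no stated analysis beyond whatever table is produced, while the supporting quantity, prevalence, gets an interval. The second hypothesis would be read from a percentage of a few dozen carriers with no statement of its uncertainty. A figure a little above 60% or 50% would look like confirmation when the data do not exclude a value at or below it.

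The wording of the second hypothesis also leaves the unit open. It could be the carrier, the isolate or the distinct serotype, and nothing says whether carriers whose strain cannot be typed stay in the denominator. PPV and PCV are named without a list of the serotypes counted under each.

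This matters beyond the present report. The Patients section intends the survey as the baseline for judging serotype replacement after vaccine introduction, and a later survey can be compared only with a share whose unit, numerator and uncertainty are stated.

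**Working it through.** **The plan's own figure.** 500 / 120,000 = 0.42%, which agrees with the stated 0.4%. The range 350–500 cannot be strictly reproduced, because no precision is printed. With n = z²p(1−p)/d², z = 1.96, p = 0.10 and an assumed d of 3 points, n = 3.8416 × 0.09 / 0.0009 = 385, inside the range. With d = 2.5 points n = 554, and with d = 4 points n = 217, both outside it. The range is thus plausible for prevalence: the half-width at 10% is 3.1 points for n = 350 and 2.6 points for n = 500.

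**Expected carriers.** 0.10 × 350 = 35 and 0.10 × 500 = 50. The plan gives 10% as a ceiling. At 5% carriage (my assumption) the counts are 17.5 and 25, taken as 18 and 25.

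**Exact (Clopper–Pearson) 95% intervals for a share near 60%.** For x of m carriers, the lower limit is the 2.5% quantile of Beta(x, m−x+1) and the upper limit is the 97.5% quantile of Beta(x+1, m−x).

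| Carriers | Observed | 95% interval | Half-width |
|---|---|---|---|
| 35 | 21 (60%) | 42.1–76.1% | 17.0 points |
| 50 | 30 (60%) | 45.2–73.6% | 14.2 points |
| 18 (5% carriage, assumed) | 11 (61%) | 35.7–82.7% | 23.5 points |
| 25 (5% carriage, assumed) | 15 (60%) | 38.7–78.9% | 20.1 points |

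Wilson intervals are slightly narrower: 43.6–74.4% for 21/35 and 46.2–72.4% for 30/50.

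**How often the bare percentage exceeds the value.** With X binomial:
- True share 60%: P(X ≥ 22 of 35) = 0.436; P(X ≥ 31 of 50) = 0.446.
- True share 55%: 0.223 and 0.197 for the same counts.
- Against the 50% value, true share 45%: P(X ≥ 18 of 35) = 0.275; P(X ≥ 26 of 50) = 0.197.

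**Results above the value whose exact interval still includes it.**
- For 60%: 22–27 of 35 and 31–37 of 50. The lower limits at 27/35 and 37/50 are 59.9% and 59.7%.
- For 50%: 18–23 of 35 and 26–32 of 50. The lower limits at 23/35 and 32/50 are 47.8% and 49.2%.

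**Effect of the denominator (illustration only).** The documents give no non-typeable rate. Assume 2 to 7 of 35 carriers (6–20%) cannot be typed. Then 21/35 = 60% with them counted, and 21/33 = 64% to 21/28 = 75% with them left out.

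**Who is a carrier.** Sample processing plans both NP and OP swabs, whereas Study procedure says one NP swab per subject. Study procedure accepts a positive PCR or ELISA, but no laboratory section describes an ELISA. Statistical Methods defines NP and OP carriage from nasopharyngeal cultures alone. These statements set the serotype denominator and do not agree.

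**The case against.** **The study is descriptive.** The Susceptibility testing section ends by saying that results are presented descriptively and not for comparison, and no test of 60% or 50% is planned. This stands as an argument against a test. It does not dispose of the interval: the scope of that sentence is unclear from its position, and the plan already gives its descriptive prevalence a confidence interval.

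**An interval does not make all values inside it equally likely.** A reader might infer that any result whose interval includes 60% supports 60% as well as the observed share. That is wrong. At 27/35 the likelihood ratio for the observed 77% against 60% is about 10 to 1, and at 37/50 about 9 to 1; only just above the value is it near 1 (1.06 at 22/35). The right statement is that such a result does not exclude 60%.

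**A no-exceedance rule would be an unplanned test.** It is tempting to forbid any claim above 60% or 50% unless the lower limit clears the value. That would be a one-sided 2.5% test under another name. With the exact interval and a true share of 70%, it would clear 60% only 13% of the time with 35 carriers (28 or more needed) and 22% with 50 (38 or more needed). The documents do not call for such a rule.

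**The sample size is not shown to be wrong.** A reader might conclude that 350–500 is too small. The documents set no precision target for the serotype shares, so all that can be said is that their precision is unstated.

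**Conclusion.** The point holds as a gap in analysis and reporting. The plan's primary objective and its second hypothesis would rest on percentages without intervals, from at most about 35–50 expected carriers for 350–500 participants. Uncertainty is about ±14 to 17 points at the 10% ceiling and about ±20 to 23 points if carriage is 5%. A bare figure above 60% or 50% often does not exclude a value at or below it.

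The sizes assume carriers behave as independent binomial observations, one per person, with the carrier as the unit. The 5% carriage and the non-typeable fraction are my assumptions. Enrolment beyond 500, which the plan allows, would narrow the intervals. The disagreement over swabs and case definition is a related matter that affects the denominator; the missing interval stands without it. The change is worth making before analysis, and nothing here calls the design into question.

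**What to change.** **In Statistical Methods, add:** *Among confirmed carriers, the proportion carrying at least one PPV serotype and, separately, at least one PCV serotype is reported with an exact (Clopper–Pearson) 95% confidence interval. The unit is the carrier, and non-typeable carriers stay in the denominator. The serotypes counted as PPV and PCV are listed before analysis. Individual serotypes are reported as counts and percentages. The 60% and 50% values are interpreted descriptively alongside the interval, with no pass/fail rule.*

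The carrier as unit is a choice the plan has not made. If the sponsor prefers isolates or serotypes, state that unit and give the same kind of interval.

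**In Sample size justification, add:** *At 10% carriage, 350–500 participants give about 35–50 carriers and a 95% interval for a vaccine-type share of about ±14 to 17 points. If carriage is 5% (assumption; 18–25 carriers), it is about ±20 to 23 points. Enrolment above 500 would give more carriers.*

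**Reconcile who counts as a carrier** across Sample processing, the laboratory sections, Study procedure and Statistical Methods: which swabs are taken, whether a positive at NP, OP or either site counts, and which laboratory result confirms a case.

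**Cost:** two extra intervals and some wording, with no added participants. The stated precision will look less favourable, and the unit and serotype lists must be settled in advance. With multiple carriage, individual serotype percentages may sum to more than 100%, and a share of carriers may differ from a share of serotypes set against the same 60% and 50%.
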